## Study Protocol

### Is the stepping-down approach a better option than multiple daily injections in patients with chronic poorly controlled diabetes on advanced insulin therapy?

#### **Methods and Materials:**

This study is an interdepartmental collaborative study among the Department of Internal Medicine, Department of Family & Community Medicine (UCSF Fresno), Sierra Vista Family Medicine Residency Program and Division of Endocrinology.

The study will be conducted at the following multiple locations in order to maximize the patient recruitment:

- (1) Internal medicine clinic at Derian Koligian ambulatory care center (ACC)
- (2) Family practice medicine clinic at ACC
- (3) Endocrine clinic at ACC
- (4) Internal medicine clinic at University Medicine Associates in East medical Plaza
- (5) Endocrine clinic at University Medicine Associates in East medical Plaza
- (6) Sierra Vista clinics

The patients will be recruited during the first 12 months of the study or until the predetermined sample size is reached, whichever comes first.

#### ***Inclusion criteria***

The patients with T2DM who met all of the following criteria were included in the study.

- (1) > 21 years of age
- (2) Body mass index (BMI)  $\geq 30$  kg/m^2
- (3) On insulin at least 2 times daily comprising both a basal and a prandial insulin or a pre-mix insulin with or without other non-insulin medications for a least past 3 months
- (4) A1c >8%
- (5) eGFR >45%

#### ***Exclusion criteria***

The patients with any of the following criteria were excluded.

- (1) Any patient who did not meet the above inclusion criteria.
- (2) Pregnancy
- (3) On a SGLT2i and a GLP1 RA or U-500 insulin at the time of enrollment.
- (4) T1DM
- (5) C-peptide below normal range if measured in the past.
- (6) A history of diabetes ketoacidosis
- (7) A history of recent and frequent ( $\geq 2$  times within past 3 months) urinary tract infection or genito-urinary candidiasis requiring antibiotic and/or anti-fungal therapies within past 3 months
- (8) A personal or family history of medullary thyroid carcinoma (MTC) or in patients with Multiple Endocrine Neoplasia syndrome type 2 (MEN 2)
- (9) eGFR <45%
- (10) A history of acute pancreatitis

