## Procedures

All participants in both groups will make a total of 3 visits over a 16-week period. The 2nd visit is at week 4 and 3rd visit at week 16 after initial visit. At each visit, all patients will have a blood test for A1c, CMP, CBC, fasting lipid and measurements of body weight, height, blood pressure, and heart rate, answered adverse reaction questions and completed the Diabetes Medications Satisfaction (DM-SAT) Questionnaire form.

At first visit, the following changes will be made in intervention group:

- (1) All prandial insulin injections (Humalog, Novolog, Apidra, Novolin R or Humulin R) will be discontinued.
- (2) Basal insulin (NPH, Lantus, Levemir, Toujeo or Tresiba) will be continued at 80 % of the home dose. The dose will be gradually increased until the patient is back on the home dose (the dose that the patient has been taking at home prior to the enrollment) or fasting BG of 80-130mg/dl was achieved by using the self-titration regimen. (Attachement#1)
- (3) If the patient is on pre-mixed insulin 2-3 times daily, it will be switched to a basal insulin alone and Glargine was given at 40% of total daily dose of pre-mixed insulin. The dose will be gradually increased until fasting BG of 80-130mg/dl is achieved by using the self-titration regimen. (Attachement#1)
- (4) Metformin at home dose will be continued, but other non-insulin diabetes medications will be discontinued. If the patient is not on metformin, then Metformin ER will be started at 500mg daily with a meal for 2 weeks and then 1000mg daily as a maintenance dose if tolerated.
- (5) Both SGLT2i, Empagliflozin 10 mg or 12.5mg once daily, and GLP1 RA, Dulaglutide 0.75mg subcutaneously once weekly, will be added to metformin and a basal insulin.

The patients will be trained on the injection technique of the once-weekly GLP1 RA and given information on potential side effects, risk and benefits of all new medications in detail, hypoglycemia management and the self-titration regimen for the basal insulin.

In the control group, the patients will be advised to remain on MDI and to have the usual and standard care through the primary care provider. They will also be advised to gradually increase the basal insulin until fasting BG of 80-130mg/dl is achieved by using the self-titration regimen as in the intervention group. (Attachement#1)

The patients in both groups will be advised to monitor FPGs daily at minimum.

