A research coordinator will make a phone call to all participants in both groups at week 1, 2, 8, and 12 to review fasting glucose measurements, ask for possible adverse events, incidents of hypoglycemia, and any change in medication.

At each visit, the patients will be questioned for adverse events (nausea, vomiting, diarrhea, headache, acute pancreatitis, bacterial or fungal genito-urinary tract infection, severe hypoglycemia with blood glucose <40, mild hypoglycemia with BG 41-69, diabetes ketoacidosis, any hospitalization for hyper or hyper-glycaemia).

At 2nd visit, Empagliflozin and GLP1 RA, Dulaglutide will be increased to maximum doses of 25mg and 1.5mg respectively if the patient tolerated the starting dose and if the additional glycemic control is required.

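### The primary A1c comparison is planned without baseline A1c as a covariate; ANCOVA would gain precision at almost no cost, and exclusion 3 needs clearer wording

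*Combined protocol and SAP*

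**What the plan says.** **Outcome and test.** Outcome measurements makes the A1c change at week 16 the primary outcome. A1c is measured at entry: "At each visit, all patients will have a blood test for A1c, CMP, CBC, fasting lipid and measurements of body weight". Statistical Analysis tests differences in means by Student's t test or ANOVA if the data look normal, and otherwise by non-parametric methods including the Wilcoxon rank-sum test. Paired tests are added for before/after comparisons. No covariate is named. Design describes 1:1 block randomization and states no stratification factor.

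**Entry drugs.** Exclusion 3 removes patients "On a SGLT2i and a GLP1 RA or U-500 insulin at the time of enrollment". Inclusion 3 admits patients on insulin "with or without other non-insulin medications for a least past 3 months". In the intervention group, item 4 of Procedures reads: "Metformin at home dose will be continued, but other non-insulin diabetes medications will be discontinued". Item 5 then says that an SGLT2i and a GLP1 RA "will be added to metformin and a basal insulin". Controls have a different instruction: "the patients will be advised to remain on MDI and to have the usual and standard care through the primary care provider". Nothing tells them to stop a non-insulin drug. The visit list names no record of entry medication. The phone calls at weeks 1, 2, 8 and 12 ask about "incidents of hypoglycemia, and any change in medication".

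**The concern.** A change score subtracts the whole baseline value, which is the best use of it only if the slope of week-16 A1c on baseline is 1. If the slope is lower, the change stays correlated with baseline, and the t test carries noise that a regression on baseline would remove. With 20 per arm this is not trivial: at SD 1, the chance difference in mean baseline A1c has a standard error of √(2/20) = 0.32 points. What is at stake is precision and power, not validity.

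The second matter is wording. Because exclusion 3 joins the two classes with an 'and', a patient on an SGLT2i alone or a GLP1 RA alone is not excluded on a literal reading, and no other criterion removes that patient. For such a patient one class is not new, baseline A1c already reflects it, and a control patient may simply continue it. The documents do not say whether this was intended.

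**Working it through.** **1. The plan's own figure.** Inputs from Statistical Analysis: mean A1c 8.5, SD 1, decline 12–15%, two-sided 0.05, power 80%, 20 per arm. Declines: 8.5 × 0.12 = 1.02 and 8.5 × 0.15 = 1.275 points. Control change is not stated and is taken as 0. The two-sample t calculation needs 17 per arm for 1.02 and 11 for 1.275. At 20 per arm, power is 88.2% and 97.5%. So 20 is more than these inputs require. The working below uses 20 per arm and 1.02.

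**2. Change score against ANCOVA.** Let r be the baseline to week-16 correlation (not in the documents; 0.3, 0.5 and 0.7 tried), with SD 1 at both visits.
- Variance of change: 2(1 − r).
- Residual variance after ANCOVA: 1 − r².
- Ratio: (1 − r²)/[2(1 − r)] = (1 + r)/2, that is 0.65, 0.75 and 0.85.

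Power is from the noncentral t with noncentrality 1.02/√(2·variance/20), on 38 df for change and 37 df for ANCOVA. The ANCOVA variance is multiplied by 1 + 1/36 for chance baseline imbalance.

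| r | SD, change | SD, ANCOVA | Power, change | Power, ANCOVA |
|---|---|---|---|---|
| 0.3 | 1.183 | 0.954 | 75.7% | 90.1% |
| 0.5 | 1.000 | 0.866 | 88.2% | 94.7% |
| 0.7 | 0.775 | 0.714 | 98.2% | 99.1% |

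The plan's SD of 1 is given for A1c itself; it is also the SD of change only when r = 0.5.

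**3. Allowing for the entry limit.** Inclusion 4 requires A1c above 8%, but a normal distribution with mean 8.5 and SD 1 puts 31% of patients below 8. Truncated at 8, its variance is 0.486 (SD 0.70). Keep the slope at r and the residual variance at 1 − r² (an assumption). The variance of change becomes (1 − r)² × 0.486 + (1 − r²).
- Slope 0.3: 0.238 + 0.910 = 1.148, SD 1.072. Power 83.5% for change, 90.1% for ANCOVA.
- Slope 0.5: 0.122 + 0.750 = 0.872, SD 0.934. Power 92.0% and 94.7%.
- Slope 0.7: 0.044 + 0.510 = 0.554, SD 0.744. Power 98.8% and 99.1%.

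Simulation agrees with both sets to within about one point (for example 84% and 91% at slope 0.3 with truncation). Under no effect, ANCOVA rejected in about 5% of simulated trials.

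**4. What prior single-class use adds.** Let q be the share of such users and suppose, as an assumption, that the effect is halved in them. The arm difference is then 1.02(1 − 0.5q). At 20 per arm and SD of change 1, 80% power needs 0.909 points, so the break-even is q = (1 − 0.909/1.02)/0.5 = 22%. At a 15% decline it is (1 − 0.909/1.275)/0.5 = 57%. In simulation at q = 20% and r = 0.5, adding a yes/no prior-use term to an ANCOVA that already has baseline A1c changed power by less than 1 point (about 89% either way).

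**The case against.** **Baseline is already handled and the test is valid.** This is correct as to validity: the outcome is a change, and randomization protects the unadjusted comparison. A reader might infer that the plan ignores baseline A1c or is biased without adjustment; the documents support neither. What stands is that subtraction uses the baseline less efficiently than regression.

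**The gain depends on assumptions.** True. The correlation is not in the documents, and respecting the A1c entry limit roughly halves the gain. At a correlation of 0.7 there is little left to gain. But the gain is positive in every case tried.

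**The tempting stronger reading concerns exclusion 3.** A reader might infer that single-class users materially dilute the effect, that nobody would know who they are, and that a prior-use covariate is needed. The documents do not support this:
- They give neither the share of such patients nor the effect in them, so dilution cannot be sized.
- Sites must know SGLT2i and GLP1 RA use to apply exclusion 3 and intervention item 4, and asking about changes in medication presupposes a starting list. What is unstated is only the recording of that use as a data item.
- A main-effect term does not repair a smaller effect in prior users. It helps noticeably only if prior users also have a different course in both arms. With an assumed 0.5-point worse outcome, q = 20% and r = 0.5, power rises from about 85% to 89%. Nothing in the documents supports that 0.5.
- The training sentence, "given information on potential side effects, risk and benefits of all new medications in detail", is not an eligibility rule and says little about intent. Item 4 stops the old drug before item 5 adds both classes, so the regimen can be delivered.

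**Conclusion.** The point holds as one of precision. The planned unadjusted comparison is valid but leaves available information unused. At 20 per arm, a 1.02-point difference and no control change, adjusting for baseline A1c is worth about 6 to 7 points of power at a correlation of 0.5 and about 14 at 0.3 with an untruncated SD of 1. With baseline truncated at 8% and the same slope and residual SD, it is worth about 3 and 7 points. These are illustrations, since the correlation is assumed.

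Exclusion 3 is a separate and lesser matter. Its literal wording leaves users of one class eligible, and the documents do not settle whether that is meant. This calls for reconciling the text; it does not show that the trial is biased or underpowered.

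**What to change.** 1. In Statistical Analysis, name the primary comparison as an ANCOVA of week-16 A1c on arm and baseline A1c, reporting the adjusted difference with its 95% confidence interval. Using change as the response gives the same arm estimate and p value, so the stated outcome need not alter.
2. Keep the t test or Wilcoxon test on change as a sensitivity analysis.
3. Reword exclusion 3 so that it says plainly whether users of one class alone are eligible, and reconcile it with intervention items 4 and 5. The investigators must decide which was intended.
4. If such users remain eligible, record SGLT2i and GLP1 RA use at the first visit and tabulate it by arm. A prior-use covariate may be added but is not needed.

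Cost: one residual degree of freedom (37 instead of 38) and no new measurement for steps 1 and 2; one clarified sentence for step 3; and for step 4 one data item that sites must look at anyway.

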## Design

This is the prospective, randomized, open-label, controlled, parallel-group study. Patients will be allocated 1:1 to either intervention (i.e. Step-Down) or control (MDI) group by using block randomization with computer-generated random sequence from <http://www.randomization.com>.

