### **Statistical Analysis:**

We will attempt to recruit and consent 20 patients in each arm that was calculated to provide an 80% statistical power at a 0.05 alpha in this continuous endpoint, two independent sample study.

The calculation was based on the following:

A mean Hemoglobin A1c of  $8.5 \pm 1\%$  at the initiation of the study period. In the treatment group we anticipate a decline in Hemoglobin A1c of 12-15% by the end of the study period. The standard deviation for the mean A1c was derived from the literature (Glucagon-Like Peptide 1 Receptor Agonist or Bolus Insulin With Optimized Basal Insulin in Type 2 Diabetes. Michaela Diamant Et al. Diabetes Care October 2014 vol. 37 no. 10. 2763-2773)

The data will be analyzed by using SPSS or similar software. Significance testing will be conducted at the two-sided 5% level. Continuous variables will be examined for normality and if assumption is met, differences in mean values will be tested using Student's t test an analysis of variance (ANOVA). If not normally distributed, non-parametric procedures will be used, including Wilcoxon rank Sum test. Categorical data will be analyzed using Fisher's exact test and Chi square analysis. Since before/after comparisons will also be performed on the same study patients, we will utilize paired t tests and McNemar's chi-square test.

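### Prior insulin regimen decides which step-down rule applies, but allocation is not stratified on it and the A1c comparison does not adjust for it; with 20 per arm this costs precision and credibility, not validity

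*Combined protocol and SAP*

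**What the plan says.** Inclusion criterion 3 admits two kinds of patient: those on a basal plus a prandial insulin, and those on a pre-mix. Prior regimen is therefore known before allocation.

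The Procedures section treats the two differently in the intervention arm. For basal-plus-prandial users (item 2), basal insulin "will be continued at 80 % of the home dose" and is raised until either the home dose or the fasting glucose target is reached. For pre-mix users (item 3), "it will be switched to a basal insulin alone and Glargine was given at 40% of total daily dose of pre-mixed insulin", with the fasting target as the only stated end-point of titration. Controls stay on their regimen and are told to raise the basal insulin by the same self-titration scheme; the section does not say how this applies to a pre-mix user.

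The Design section allocates patients 1:1 "by using block randomization with computer-generated random sequence". It names no stratification factor and no block size. Under Statistical Analysis, the target is stated as "We will attempt to recruit and consent 20 patients in each arm", and means are compared by t test or ANOVA, or by a Wilcoxon test if the data are not normal. No covariate is named.

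**The concern.** Prior regimen is a recorded baseline factor that determines part of what a patient receives if allocated to step-down. In a trial of 40, unstratified blocks equalise the arm sizes but do nothing to equalise the regimen mix. If the arms differ visibly on this factor and regimen is related to A1c change, the unadjusted estimate will sit some way from what a balanced trial would have shown. In an open-label trial, whether to adjust would then be argued after the results are known. At stake are some precision and the ease of defending the result.

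**Working it through.** **1. The plan's own figure.** The inputs, from Statistical Analysis, are a baseline A1c of 8.5 with SD 1, a 12-15% decline in the treated arm, 80% power and a two-sided 5% level. The decline is 0.12 × 8.5 = 1.02 to 0.15 × 8.5 = 1.275 points. The plan states no change for controls; I assume none. With n = 2(1.96 + 0.84)²SD²/δ² per arm:

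- δ = 1.02: n = 16 (17 with the exact t distribution).
- δ = 1.275: n = 10 (11 with the exact t distribution).

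Twenty per arm is not reproduced from these inputs, but it errs on the cautious side: exact-t power at 20 per arm is 88% to 98%. The checks below take 20 per arm as given.

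**2. Chance of imbalance at the design stage.** The number of pre-mix users to be enrolled is not known in advance. If a share p of eligible patients use pre-mix, independently of order of entry, the counts X₁ and X₂ in the two arms are independent Binomial(20, p). A 20-point difference is 4 patients of 20, and 30 points is 6.

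| Assumed share p | P(difference of 4 or more) | P(difference of 6 or more) |
|---|---|---|
| 10% | 6.3% | 0.4% |
| 20% | 16.4% | 2.9% |
| 30% | 22.6% | 5.6% |
| 40% | 25.8% | 7.5% |
| 50% | 26.8% | 8.1% |

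The chance peaks at p = 50%. Simulated unstratified blocks of 4, 8 and 10 gave the same values to within about half a point (16-17% at a 20% share, 27% at 50%), so block size hardly matters here.

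**3. The same question with the pre-mix total fixed.** If exactly K of 40 patients use pre-mix, the count in one arm is hypergeometric. P(difference of 4 or more) is 0.301 at K = 12, 0.333 at K = 16 and 0.343 at K = 20. At odd totals a difference of exactly 4 cannot occur, and the chance is 0.155 (K = 11), 0.176 (K = 13), 0.191 (K = 15) and 0.205 (K = 19).

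**4. Size of the shift.** Let g be the difference in A1c change between regimens; the documents give no value, and I take 0.5-1.0 as an assumption.

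- Regimen acts equally in both arms: shift = 0.20 × g = 0.10 to 0.20 points.
- Regimen acts only in the intervention arm: take 12 pre-mix users split 8 and 4. The arm with 8 has 40% pre-mix against 30% overall, 10 points off. Shift = 0.10 × g = 0.05 to 0.10 points.

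The standard error with SD 1 is √(2/20) = 0.316, so the both-arms shift is 0.32 to 0.63 of a standard error. This applies the plan's SD for A1c to the change in A1c, which is a further assumption.

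**5. What stratified lists achieve.** With separate 1:1 lists by regimen and 40 patients, the largest possible imbalance is 5 points with blocks of 2, 10 with blocks of 4 and 14 with blocks of 6. With blocks of 8 or 10, a 20-point imbalance is possible but occurred in under 0.1% of simulated trials.

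**6. What the model term gains and costs.** With balanced arms, a regimen factor removes p(1 − p)g² from the residual variance and one degree of freedom (38 to 37). At δ = 1.02, SD 1 and p = 20-50%, the change in power from 88.2% is:

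- g = 0: a loss of less than 0.1 point.
- g = 0.5: a gain of 1.2 to 1.9 points.
- g = 1.0: a gain of 4.7 to 7.1 points.

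If the term is added after unstratified allocation, chance imbalance also inflates the variance: the mean squared correlation between arm and regimen is 1/39 = 2.6%. The loss at g = 0 is then about 0.9 point.

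**The case against.** A reader might infer that a 20-point imbalance is likely, or arises in about one trial in three. The one-in-three figure requires fixing the final pre-mix total at an even number of roughly 12 to 28 out of 40. The documents fix no such total, and once its uncertainty is included no share gives more than 27%. That is not a likely event.

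A reader might also infer that the primary comparison is biased. It is not. Randomisation keeps the t test valid on average, and variation due to regimen mix is already in its standard error.

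The two regimens also have much in common. Both lose prandial insulin, follow the same rules for metformin and the two added drugs, and use the same self-titration scheme toward the same fasting target. What differs is the starting basal dose and, for basal users, an alternative end of titration. Nothing in the documents shows that this changes week-16 A1c by 0.5-1.0 points. A difference that acts only in the intervention arm is effect modification: it halves the shift, and a main-effect term does not model it.

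Finally, with six listed clinic locations and baseline A1c available, other factors could be proposed instead, and simple blocks are an acceptable choice at this size.

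Most of this stands and limits the weight of the point. It does not remove the gap: a factor known at entry, tied by the plan itself to how treatment is given, is neither balanced nor adjusted for, and closing the gap costs little.

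**Conclusion.** The point holds as a minor, optional improvement. An imbalance of 20 points or more in prior regimen would arise in about 16-27% of trials if the pre-mix share is 20-50%, and less often if it is lower. Its effect on the estimate would be 0.10-0.20 A1c points if regimen acts in both arms with g of 0.5-1.0, or 0.05-0.10 if it acts only under step-down, against a standard error of about 0.32 and an anticipated effect of 1.02-1.275 points. The pre-mix share, the value of g, the absence of change in controls and the use of SD 1 for change are all assumptions. If regimen does not predict A1c change, nothing is lost by the present plan.

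**What to change.** Before allocation starts, generate two 1:1 lists with small blocks, one for basal-plus-prandial users and one for pre-mix users, and prespecify prior regimen as a factor in the primary A1c comparison (ANOVA with arm and regimen). If the rank test is used instead, specify its stratified form (van Elteren). If allocation has already begun, leave the list alone and prespecify the model term only, before any outcome comparison. I would not add a treatment-by-regimen interaction to the primary analysis in 40 patients; regimen-specific estimates can be reported descriptively.

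The sponsor should also clarify how the control-arm titration instruction applies to pre-mix users, so that the factor means the same thing in both arms.

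The cost is a second list to administer, an incomplete final block in each list, and one degree of freedom. If regimen turns out not to be prognostic, the power lost is about 0.1 point at most with stratified lists and about 0.9 point if only the term is added. No dose or clinical rule changes.
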